#### 13.4 Missing, Unused or Spurious Data

Missing data that cannot be retrieved from source records or other repositories will be recorded as such in the CRFs and will not be entered into the statistical analysis. Spurious data will be examined by the Sponsor's monitor, medical or statistical advisors and a decision made as to how it should be handled. If there is an obvious transcription or data entry error such as a misplaced decimal point in a biochemical parameter this will be discussed with the CRO or the laboratory and, if all parties agree, it will be corrected and endorsed by both the PI and the Sponsor. Outlying data may be treated appropriately after consultation with the Sponsor's statistical advisors (e.g. isolated, out of range biochemical parameters where there may have been a recording error may be treated by removal of highest and lowest observations and re-analysis. In such an event both the fact will be recorded in the statistical report and data will be presented showing the full data set and after removal of paired outliers).

Unused data (e.g. superfluous blood pressure recordings or haematological results in addition to those required by the protocol will remain part of the source documentation and only be incorporated into the trial documents and analysis if there is reason for them to be (e.g. an unexpected fall in blood pressure that might constitute an AE).

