#### 3.1 Endpoints

Safety:

- Frequency, type and relationship to treatment of AEs and SAEs
- Out of range laboratory parameters (haematology and chemistry)
- Vital signs
- ECG abnormalities Day 0 Day 90

Primary efficacy endpoint:

• Serum lactic dehydrogenase (LDH) AUC from Day 0 to Day 28 compared with 28 days pre-treatment

Secondary efficacy endpoints:

- Haemoglobin at Day 28 and day 90 and Day 180, absolute and change from baseline
- LDH at days 90 and 180
- Haptoglobin at day 28, day 90 and day 180, absolute and change from baseline
- Dependency on blood transfusion
- Quality of Life at days assessed by the FACIT and EORTC QL-C30 instruments compared to Day 0, day 28, 90 and 180

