All patients will return to the hospital out patient clinic for follow-up at a minimum of monthly intervals according to the schedule in appendix 1.

Blood and urine samples will be taken from all patients according the schedule on appendix 1.

Patients who have satisfactorily mastered the technique of self-administration of Coversin may be discharged home when considered appropriate to do so by the PI providing that adequate arrangements for daily pre-dose blood sampling and sample handling for CH50 samples have been arranged (see below).

All patients will be followed up at a minimum of monthly intervals by the PI. If at the 6 month follow-up the patient wishes to continue Coversin treatment and if the PI is satisfied as to the suitability of Coversin treatment, the patient may be transferred to the long-term follow-up protocol.

It is expected that the majority of patients will respond to an ablating dose of 0.57mg/kg followed by a daily maintenance dose of 25% of the ablating dose.

On a per patient basis this will be adjusted as necessary on the basis of clinical response and CH50 assay. The protocol allows for a flexible, tailored dose adaptation on day 7 and any subsequent follow-up. in patients who are not adequately controlled as is outlined below ..

If patients are not adequately controlled at the first (7 day) or subsequent follow up either of three options may be followed:

Patient will be reinduced with an identical ablating dose (0.57 mg/kg) and /or the maintenance dose may be increased with one step at the time for a maximum of 2

times according to the below schedule of increments . Each incremental dose level must be given for a minimum of 4 days.

The definition of adequately controlled coversin treatment is:

LDH <1.5xULN AND CH50 <10% of baseline.

It is expected that this adequate control is achieved at day 5.

If a recent CH50 result is not available at the time of assessment then the PI will make a decision on clinical grounds alone on the adequacy or otherwise of disease control.

If adequate control is not achieved on day 5 of maintenance therapy at the standard dose level (and day 5 of increment dose levels if applicable) the following dose adaptation will take place:

- If CH50  $\leq 10\%$  and LDH is reducing but still  $\geq 1.5xULN$ , treatment at the same maintenance dose level is continued for another week.

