#### 6.1 Endpoints

Primary Efficacy Endpoint:

• Significant reduction in mean serum LDH from Day 0 (pre-dose) to Day 28 (AUC)

Secondary Efficacy Endpoints:

- Change in LDH from Day 0 (pre-dose) at monthly intervals after Day 28
- Change in proportion of PNH clone Day 0 Day 90
- Change in mean Hb Day 0 Day 90
- Change in mean Hp Day 0 Day 90
- Change in FACIT score Day 0 day 28- Day 90 Day 180
- Change in EORTC QLQ C30 score Day 0 -Day 28-Day 90 Day 180

Safety Endpoints:

- Frequency, type and relationship to treatment of AEs and SAEs
- Out of range laboratory parameters (haematology and chemistry)
- Vital signs
- ECG abnormalities Day 0 Day 90

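### The Section 13.4 outlier option removes both the highest and lowest value; in a falling LDH series these tend to be the pre-dose value and best response, and no governing analysis is named

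*Combined protocol and SAP*

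**What the plan says.** Section 13.4 deals with obvious transcription or entry errors first: they are corrected once all parties agree. It then turns to values that are only suspected. The general permission is "Outlying data may be treated appropriately after consultation with the Sponsor's statistical advisors". The worked example covers "isolated, out of range biochemical parameters where there may have been a recording error", and such values "may be treated by removal of highest and lowest observations and re-analysis". The report must record that this was done, and "data will be presented showing the full data set and after removal of paired outliers".

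The section gives no numerical criterion for an outlier and no timing for the decision. It does not define the set from which highest and lowest are taken (one patient's series, one visit, or all patients pooled). It does not say which of the two analyses supports the conclusion.

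The affected endpoints are these. Section 3.1 defines the primary efficacy endpoint as "Serum lactic dehydrogenase (LDH) AUC from Day 0 to Day 28 compared with 28 days pre-treatment"; Section 6.1 also frames it as a Day 0 to Day 28 LDH reduction by AUC. Both sections list out-of-range haematology and chemistry results as a safety endpoint. Section 13.1 plans per-patient linear regression if fewer than four patients are recruited. With four or more it plans paired t-tests between timepoints, giving Day 0 and Day 28 as the example, plus a mixed model.

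**The concern.** Removing a matched pair of extremes makes some sense for repeated readings scattered around a stable level. LDH here is not expected to be stable. The synopsis requires at least 1.5 x ULN at entry, and Section 6.0 defines adequate control as "LDH <1.5xULN AND CH50 <10% of baseline". If treatment works, the highest value tends to be the pre-dose one and the lowest the best response, and the treatment effect is largely read from those two values.

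The trigger does not discriminate well either. Every patient enters with LDH above the normal range, so being out of range is the expected state at baseline. If a suspect value breaks the trend but is neither the highest nor the lowest, the option as written keeps it and removes two values that nobody questioned.

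The decision involves the sponsor's advisers in an open-label study of one to six patients, with no criterion fixed beforehand. If the full and trimmed results disagree, Section 13.4 leaves open which one is believed.

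**Working it through.** The plan states no power or effect-size figure to reproduce. The check is an illustration of what the option does to an LDH series and to the planned tests.

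**Inputs from the protocol.** Entry LDH at least 1.5 x ULN (synopsis); target below 1.5 x ULN (Section 6.0); window Day 0–28 (Sections 3.1 and 6.1); regression or paired t-test (Section 13.1); p < 0.05 (Section 13.3, taken as two-sided).

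**Assumptions, not in the protocol.** LDH(t) = 1.3 + 3.7·exp(−kt) in units of ULN, starting at 5.0, without noise, with k = 0.2 (fast) or 0.1 (slower) per day. The visit days in Appendix 1 are not available in the text reviewed, so two patterns were tried: weekly (0, 7, 14, 21, 28) and eight visits (0, 1, 2, 5, 7, 14, 21, 28).

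**Step 1: which values go.** In all four series the highest is Day 0 and the lowest is Day 28. The remaining span is Days 7–21 (weekly) or Days 1–21 (eight visits). Neither change from Day 0 nor an AUC covering Days 0–28 can then be formed.

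**Step 2: slope = Sxy/Sxx, full and trimmed (x ULN per day).**

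| Visits | k | Full | Trimmed | Trimmed ÷ full | Regression p |
|---|---|---|---|---|---|
| Weekly | 0.2 | −57.61/490 = −0.118 | −6.00/98 = −0.061 | 0.52 (48% flatter) | 0.080 to 0.21 |
| Weekly | 0.1 | −58.34/490 = −0.119 | −9.69/98 = −0.099 | 0.83 (17% flatter) | 0.021 to 0.12 |
| Eight | 0.2 | −88.95/739.5 = −0.120 | −41.70/299.3 = −0.139 | 1.16 (16% steeper) | 0.006 to 0.016 |
| Eight | 0.1 | −91.48/739.5 = −0.124 | −42.76/299.3 = −0.143 | 1.15 (15% steeper) | 0.0003 to 0.0016 |

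The p-values reflect only lack of fit to a straight line, since no noise was added. In one case (weekly, k = 0.1) the two analyses fall on opposite sides of 0.05. With eight visits both stay below it.

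**Step 3: range of observed LDH (x ULN).** Weekly: 3.7 to 0.9 (k = 0.2) and 3.5 to 1.4 (k = 0.1). Eight visits: 3.7 to 3.0 and 3.5 to 2.9.

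**Step 4: time-averaged AUC, k = 0.1, trapezoid rule.** Weekly, full: 7 × (5.000/2 + 3.137 + 2.212 + 1.753 + 1.525/2)/28 = 2.59. Trimmed, Days 7–21: 7 × (3.137/2 + 2.212 + 1.753/2)/14 = 2.33. With eight visits the same rule gives 2.57 over 28 days and 2.78 over the remaining 20. The direction again depends on the visit days.

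**Step 5: sensitivity to the assumptions.** A wider set was also tried: start at 3 or 8 x ULN, floor 1.2, half-life 3, 7 or 14 days. Weekly slopes flatten by 5–56% and eight-visit slopes steepen by 10–15%. With 10% noise added, Day 0 is the highest value in 91–100% of weekly series but only 43–91% of eight-visit series. Day 28 is the lowest in 41–95% and 42–95%.

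**Step 6: paired t-test, worst case.** If trimming is pooled over four patients, and takes Day 0 from one and Day 28 from another, two pairs remain. The two-sided 5% critical t rises from 3.18 (3 df) to 12.71 (1 df). If both values come from one patient, three pairs remain (4.30). Starting from six patients, four pairs remain (2.57 to 3.18).

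**The case against.** The strongest defence is that this is an optional example confined to isolated, possibly misrecorded values, and that it protects the full data. The trimmed run is called a re-analysis, it must be recorded, and the full data set must be shown beside it. Sections 13.1 and 13.6 point to using every measurement taken while the protocol was followed. An orderly fall in LDH is not an isolated suspect value. All of this stands and limits the point. It does not supply the missing sentence on which result governs, and it does not make removal of the opposite extreme a sound response to one doubtful value.

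Four stronger readings are tempting, and the protocol does not support them.

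- A reader might infer that out-of-range safety results are deleted. They are not: the full data set is reported, and Sections 12.1 and 12.2 capture abnormal laboratory findings as adverse events independently. What is missing is an explicit exemption for the endpoint "Out of range laboratory parameters (haematology and chemistry".
- A reader might infer that a valid value is always lost. The reference to paired outliers could describe a case where both removed values are suspect.
- A reader might take the 48% flattening as the expected effect. It needs weekly-only sampling, which fits poorly with Section 6.0: daily visits until stabilisation, and control, including LDH, judged at day 5 and at the 7-day follow-up. With early visits the slope steepens instead.
- A reader might take four patients becoming two as typical. It requires pooled trimming with the extremes in different patients, and the mixed model in Section 13.1 does not need complete pairs.

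**Conclusion.** The point holds in a limited form. Section 13.4 offers an unsuitable method for a suspected error: it normally sacrifices an unquestioned value, and in an LDH series that falls as intended it tends to remove the values carrying the comparison with Day 0. It also leaves the governing analysis unstated and gives no exemption for safety laboratory data.

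The size cannot be fixed from the protocol. Under the assumed curves the slope moves between 48% flatter and 16% steeper, depending mainly on the visit days; the early-visit pattern is the more plausible given Section 6.0. Because the shift can go either way, no consistent bias for or against the drug can be claimed. The mandatory display of both data sets, and the pointers elsewhere to using every measurement, keep the consequence modest. This is a cheap improvement.

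**What to change.** Replace the paired-extreme option in Section 13.4 with three statements.

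1. A value is excluded or corrected only when source or laboratory verification documents an error, and then only that value is changed. The opposite extreme is left alone.
2. The full verified data are primary for LDH and for all safety laboratory summaries. No laboratory value is left out of a safety summary merely for being extreme.
3. Any analysis omitting unverified outliers is a labelled sensitivity analysis, reported beside the primary result.

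The cost is one rewritten paragraph, with no change to visits, samples or patient numbers. The downside is that an odd value that cannot be verified as an error stays in the primary analysis and, with one to six patients, may be influential. The sensitivity analysis will show that openly.

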## 13.5 Deviations from the Statistical Plan

It is not envisaged that there should be any deviations from the statistical plan since this is primarily a safety study. Any unexpected deviations (eg a requirement for a trend analysis not foreseen in planning the trial) will be discussed with the PI and the statistical advisor and the rationale for such an analysis will be included in the trial report.

## 13.6 Subjects to be Included in the Analysis

All patients in the study will be included in the safety analysis whether completing the trial according to the protocol or not. The efficacy analysis will include all measurements made whilst the patient(s) correctly followed the trial protocol.

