## 5.0 SUBJECT WITHDRAWAL CRITERIA

Subjects may be withdrawn from the trial in the following circumstances:

• An adverse event graded serious or severe which in the opinion of the PI is possibly, probably or definitely related to administration of the trial drug.

- Any other reason for which, in the opinion of the PI it would not be in the best interests of the subject to remain in the trial.
- At the request of the subject for any reason.
- Non-compliance or behaviour not compatible with the proper conduct of the trial.

Appropriate clinical and serological data will be entered in the CRFs. In addition the Subject Withdrawal page of the CRFs will be completed. All data that would normally have been entered on the final day of dosing will be collected and entered together with such additional data as the PI considers clinically necessary to ensure the subject's safety or to elucidate the nature of the AE (e.g. special tests, X Rays, scans, photographs etc.)

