- If LDH is decreasing and if CH50 is between 50 and 10% of baseline, the maintenance dose may be increased according to the schedule of increments of maintenance dose shown below.
- If LDH is not reducing and CH50 is >50% of baseline the patient must either be discontinued from the trial and switched to alternative therapy or must be readmitted to hospital for dose stabilisation following another ablating dose (0.57mg/kg) of Coversin. In either case the findings and course of action must be discussed by a Trial Steering Committee comprised of, at minimum, the PI, and the Medical Director of the Sponsor company.

The schedule of increments for the maintenance dose is as follows:

Ablating dose	First maintenance	Second mainte-	Third mainte-
	dose level	nance dose level	nance dose level
0.57 mg/kg	0.14 mg/kg	0.29 mg/kg	0.57 mg/kg

Within each patient the first incremented maintenance dose should be given at 24 hour intervals for at least 4 days until steady state is reached and at that point a CH50 assay should be performed. If the CH50 is not  $\leq 10\%$  of baseline (adjusted to 100%) then the next incremental dose (Second maintenance dose level should be given for at least another 4 days before switching to the Third maintenance dose level. If at any

stage the CH50 is >50% of baseline another ablating dose should be given before using the next incremental dose.

[figure not shown]
Blood samples and timing is shown in Appendix 1. Samples for CH50, antibodies and drug level should be processed as shown in Section 20 and sent to the Akari Therapeutics Plc complement laboratory for assaying. All other laboratory tests should be done locally in the PI's hospital laboratory.

If an ablating dose is repeated , PK/PD and other assessment will be performed as indicated in Appendix 1 at 1hr, day 2 and day 5.

At increments of the maintenance dose PK and PD and other assessments are repeated at day 5 as indicated in Appendix 1.

Extra samples for PK/PD may be taken at the discretion of the investigators during illness or infection.

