#### Flow chart: Schedule of Procedures and Visits

The trial will continue for 6 months or until it has been decided by the PI in consultation with the Sponsor Company that further Coversin treatment is futile or not in the patient's best interests. If the patient is satisfactorily controlled and wishes to continue on Coversin he/she will be permitted to enter the long-term follow-up study. Drug will, if necessary, be supplied free of charge by the Sponsor until it is approved for this indication and reimbursed through the normal channels.

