#### **13 STATISTICS**

#### **13.1** Statistical Methods

The statistical approach taken will depend on the number of patients recruited.

If less than 4 patients are recruited, each patient will be analysed separately. Changes in the primary efficacy outcome during the period Day 0 to Day 28 will be analysed using linear regression using all measurements in the analysis. Secondary efficacy outcomes measured multiple times will be analysed in an equivalent manner.

If 4 or more patients are recruited, the patients will be analysed as a single group. Differences between specific timepoints (e.g. Day 0 and Day 28) for the primary and secondary efficacy endpoints will be performed using the paired t-test.

Additionally the change in the primary efficacy outcome over time will also be examined using all measurements. Mixed model will be used to allow for repeat measurements from the same patients, with the patient considered as a random effect.

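### With four or more patients, one stopped for lack of effect before Day 28 drops out of the paired and AUC results for LDH, which then lean towards benefit

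*Combined protocol and SAP*

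**What the plan says.** **Endpoint.** Section 3.1 defines the primary efficacy endpoint as the LDH AUC over Day 0 to 28 against the 28 days before treatment. Section 6.1 words it as a significant fall in mean LDH from Day 0 to Day 28, by AUC. Section 13.3 sets p < 0.05.

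**Analysis.** With four or more patients, section 13.1 pools them: "Differences between specific timepoints (e.g. Day 0 and Day 28) for the primary and secondary efficacy endpoints will be performed using the paired t-test". It adds an analysis of all measurements: "Mixed model will be used to allow for repeat measurements from the same patients, with the patient considered as a random effect". With fewer than four, each patient has a separate regression on all measurements.

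**Data used.** Section 13.6: "The efficacy analysis will include all measurements made whilst the patient(s) correctly followed the trial protocol". Section 13.4, on missing data that cannot be retrieved: it "will be recorded as such in the CRFs and will not be entered into the statistical analysis".

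**Exits.** Section 6.0: "If LDH is not reducing and CH50 is >50% of baseline the patient must either be discontinued from the trial and switched to alternative therapy". The same sentence offers a second option, readmission with a further ablating dose. The text under the flow chart also lets the trial end for a patient once it is decided that "further Coversin treatment is futile". Section 5.0 adds other reasons, for example "At the request of the subject for any reason". On withdrawal, "All data that would normally have been entered on the final day of dosing will be collected and entered". No section gives those data a role in the efficacy analysis.

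**The concern.** The section 6.0 exit is triggered partly by LDH, which is the primary efficacy outcome. A patient who leaves by that route before Day 28 is missing because the drug did not lower LDH. If the paired test and the AUC use only patients with data to Day 28, the failures are removed and the successes stay. With four to six patients one removal carries much weight, and because section 6.1 words the endpoint in terms of significance, a verdict is planned as well as a description.

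**Working it through.** The plan gives no power, effect size, SD or dropout figure, so there is none of its own to reproduce. The check has four steps.

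**1. Can the exit fall before Day 28?** Section 3.0 puts the ablating dose on day 1 and maintenance from day 2. Section 6.0 sets the check at day 5 of maintenance, which is Day 6. It allows at most two increments of at least 4 days each. At 4 to 5 days per increment and no delay for results, later checks fall on Day 10-11 and Day 14-16. So yes.

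**2. What is left of that patient?** Values before the stop were taken on-protocol, so 13.6 keeps them. The Day 28 pair does not exist, and the AUC ends at the stop. 13.4 leaves the gap empty.

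**3. Paired test.** Assumed inputs, not document figures: equal baselines; responders' mean change m = -70% with SD s = 5, 10 or 15 points; k of n patients stopped, each with true change f; two-sided test.

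- As planned: t = |m| / (s/√(n-k)), with n-k-1 degrees of freedom.
- All treated: M = ((n-k)m + kf)/n; SD² = [(n-k-1)s² + (n-k)(m-M)² + k(f-M)²]/(n-1); t = |M| / (SD/√n), with n-1 degrees of freedom.

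Example, 1 of 4, s = 10, f = 0: M = (3 × -70 + 0)/4 = -52.5. SD² = [2×100 + 3×17.5² + 52.5²]/3 = 1291.7, so SD = 35.9. t = 52.5/17.97 = 2.92 and p = 0.061. As planned: t = 70/(10/√3) = 12.1 and p = 0.007.

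| Stopped | p as planned (mean -70%) | f | Mean, all treated | p, all treated |
|---|---|---|---|---|
| 1 of 4 | 0.002-0.015 | -10% | -55.0% | 0.036-0.043 |
| 1 of 4 | 0.002-0.015 | -5% | -53.8% | 0.046-0.054 |
| 1 of 4 | 0.002-0.015 | 0% | -52.5% | 0.059-0.066 |
| 1 of 4 | 0.002-0.015 | +20% | -47.5% | 0.126-0.134 |
| 1 of 5 | 0.0001-0.003 | 0% | -56.0% | 0.017-0.021 |
| 1 of 5 | 0.0001-0.003 | +20% | -52.0% | 0.045-0.051 |
| 1 of 6 | below 0.001 | 0% | -58.3% | 0.004-0.006 |
| 1 of 6 | below 0.001 | +20% | -55.0% | 0.015-0.018 |
| 2 of 6 | 0.0001-0.003 | 0% | -46.7% | 0.026-0.030 |
| 2 of 6 | 0.0001-0.003 | +20% | -40.0% | 0.090-0.096 |

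With responders at -50% or -80% (s = 10), 1 of 4 and f = 0 give p = 0.013 or 0.005 as planned, against 0.065 or 0.061. With s = 30, the planned test for 1 of 4 is already at p = 0.056, so there is no verdict to lose.

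**4. AUC.** Assume weekly LDH (Appendix 1 is not readable) and a pre-treatment level equal to Day 0. By the trapezoid rule on Days 0, 7, 14, 21 and 28, a responder's AUC change is -35.0% if the fall is linear, or -61.25% if it is complete by Day 7. Counting one failure of four at 0% multiplies these by 3/4, giving -26.3% or -45.9%. Two of six multiplies them by 4/6, giving -23.3% or -40.8%.

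A raw AUC cut at the stop would err further. With constant LDH, a stop at Day 7 covers 7/28 = 25% of the period and a stop at Day 14 covers 50%. Against 28 pre-treatment days these would show false falls of 75% and 50%.

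**The case against.** The strongest reply is that the problem is conditional and partly handled.

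- **It may not arise.** It needs at least four recruits in a trial that may have one, and an exit before Day 28. Section 6.0 requires both LDH not reducing and CH50 above 50% of baseline, and it allows readmission instead. This stands and limits the importance.
- **Other analyses keep the patient.** The mixed model uses the early values, and below four patients the regression shows the failure. This also stands. A reader might infer that every efficacy analysis is biased towards benefit. The documents do not support that: the size and direction for the mixed model depend on a random-effects structure that 13.1 does not state beyond patient. But that model is additional and does not repair the paired or AUC result.
- **Section 13.6 does not exclude failures.** A reader might infer that it does. It does not: a patient stopped as section 6.0 prescribes was on-protocol until then. The gap comes mainly from 13.4 and from the absence of a rule for the final-day value.
- **The change of verdict is fragile.** It does not occur for 1 of 4 at -10%, nor for 1 of 5 or 1 of 6 at 0%. LDH that is not reducing at a check may still lie below Day 0. This stands: the shift in the mean is robust, the change of verdict is not.
- **Day 28 is given only as an example, and Appendix 1 cannot be read.** An early-termination LDH may be scheduled. Even so, the AUC to Day 28 is the defined endpoint, and no readable text says how such a value would enter it.

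**Conclusion.** The point holds for the paired and AUC analyses with four or more patients and at least one stop for lack of effect or futility before Day 28. Those results then describe the remaining patients and lean towards benefit. On the assumed inputs, one uncounted failure with unchanged LDH overstates the mean fall by 17.5 points (1 of 4), 14 points (1 of 5) or about 12 points (1 of 6). The verdict at p < 0.05 changes for 1 of 4 at 0%, and for 2 of 6 only if LDH rose; 1 of 5 at +20% is borderline.

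Stops for other reasons leave the same gap, but their direction is not known, and no bias towards benefit should be read into them. Section 13.5 calls this primarily a safety study, all patients enter the safety analysis, and the synopsis lists only descriptive statistics. Importance is therefore minor to moderate. The sizes rest wholly on assumed LDH changes; the gap itself rests on the text.

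**What to change.** In 13.4 and 13.6, for four or more patients:

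- **Main analysis.** The paired and AUC efficacy analyses include every treated patient. For a patient stopped before Day 28, use the final-day LDH, or if there is none the last LDH before any switch to alternative therapy, for Day 28 and for the rest of the AUC period.
- **AUC.** Never compare a truncated, un-normalised AUC with a 28-day pre-treatment AUC.
- **Sensitivity analysis.** For stops due to lack of effect or futility, use the higher of Day 0 and final-day LDH. This should not be the main rule, because it overrides observed data: in the 1 of 4 case it would reset a failure at -10% to 0% and by itself move p from 0.036-0.043 to 0.059-0.066.
- **Supportive.** Keep the on-protocol (completers) analysis and the mixed model on observed values.
- **Reporting.** Beside the result, give the number stopped, the reasons, and each patient's LDH course.

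The cost is wording only, with no extra sample and no change to any dose or clinical rule. The assigned value is an assumption and must be stated as one, and the reported effect may be less favourable. For example, one linear responder of six stopped on Day 14 for another reason would give (5 × -70 - 35)/6 = -64.2% instead of -70%. Two of six stopped for futility at -10% would give (4 × -70 + 2 × -10)/6 = -50.0%, and -46.7% in the sensitivity analysis.
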